The RELIEF™ Ureteral Stent – Assessment of Retrograde Urinary Reflux and Distal Coil Bladder Position

NCT03266770

11/29/2021

Objectives

Primary Objectives:

• Evaluation of the stent placement and the adequacy of short term drainage (defined as the presence of the stent in the ureter and the lack of surgical or other intervention to treat symptoms associated with the stent itself on the stented side during the first 48 hours).

Secondary Objectives:

- Assessment of retrograde urine reflux after placement of the RELIEF® Ureteral Stent using cystography after contrast gravity-filling of the bladder and assigning a urinary reflux grade based on:
 - o Grade I: urine refluxes into the ureter only.
 - o Grade II: urine refluxes into the ureter and up to the kidney without dilation.
 - o Grade III: urine refluxes into the ureter and kidney and causes mild dilation.
 - Grade IV: urine refluxes into ureter and kidney and causes dilation without twisting of the ureter.
 - Grade V: urine refluxes into ureter and kidney and causes significant dilation with twisting of the ureter.
- Visualization of distal coil in bladder, after RELIEF Stent placement. Document placement using a cystoscope and obtain image, if possible.
- Assessment of adverse events (incidence, relationship to device, severity) attributed to the
 Ureteral Stent, compared to established adverse event rates from published clinical studies and
 FDA reportable event occurrences, compared to number of US annual ureteral stent
 placements.
- Reporting the Ureteral Stent Symptoms Questionnaire before stent placement, after placement and prior to removal.

Background

[figure not shown]
Traditional ureteral stents are commonly used in practice to relieve renal obstruction or as a scaffold to promote healing after endoscopic or open/laparoscopic surgeries involving the ureter [1]. However, there are a lot of morbidities that can be associated with placing these stents either due to irritation of the bladder or affection the kidney.

The most commonly reported symptoms include urgency, urinary frequency, dysuria, incontinence, hematuria, suprapubic discomfort, fever due to urinary tract infections and flank pain and they can occur in up to 80% of stented patients. Sometimes, the symptoms are poorly tolerated and can negatively affect the patient quality of life [2, 3].

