All subjects should be familiar with the Informed Consent and its content, and have been given opportunity to have their questions answered about the study prior to signing the Informed Consent. At the time of admission, the patient will be assessed for suitability. If the patient meets the inclusion/exclusion criteria, he/she will enter the study.

Results will be shared with ONLY the research participants' doctors who are among the approved study team by the UH IRB.

Study Design

Allocation: Non-randomized

Endpoint Classification: Safety/Efficacy Study

Intervention Model: Single Group Assignment

Masking: Open Label

Primary Purpose: Treatment

Study Procedures

Informed Consent: Eligible subjects will be consented by a Research Nurse or Investigator prior to the procedure.

Inclusion Criteria: Confirmation of fulfilling Inclusion criteria (e.g., consent, examination, indication) and that subject does not have any Exclusion criteria.

Pre-Stenting Evaluation (Day 0 or within 24 hours of Day 0): USSQSurvey and 10 -Point Pain Score: Subject completesUSSQsurvey for baseline evaluation (pre-stenting, Day 0)

Ureteral Stenting Procedure (Day 0):

Pre-stent cystogram

- Instill dye (up to 300 cc) under gravity-filling cystogram for assessment of pre-stent reflux and capture Xray image (with C-arm). (Exclude patients with reflux). Cystogram image will be saved.
- Drain bladder

[CRF: Pre-Stent Reflux Result; Pre-Stent Cystogram Image]

Ureteral Stent Placement

- Obtain retrograde pyelogram.
- Insert guidewire and perform ureteroscopy for treatment when needed. (Based on the urologist's discretion, if trauma has been induced to the distal ureter due to ureteroscopy maneuvers, these patients will be excluded).

- Any remaining contrastshould be flushed by irrigation ofsaline. Confirmatory X-ray image may be captured to ensure that contrast has been adequately removed (Note: If residual contrast considered not acceptable or confirmatory X-ray not recommended, subject may be excluded from study and traditional stent used).
- Remove the pull-outsuture, then place RELIEF stent under cystoscopy. Stent with pusher placed over guidewire and inserted. Position pusher until reach 4 cm mark. Remove wire. Back-out pusher. Confirm xray image ofstent position and save the image.

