• If possible, subject will complete USSQ and 10-point pain scale surveys 1-2 days afterstent removal. If unusual level of pain or other potentially serious complications suspected, subject will be asked to come in for office visit and Clinician evaluation. [CRF: Record direct or remote subject evaluation and any unusual/ unexpected observation(s). Obtain successfully completed in situ USSQ survey (attach to CFR) and record 10-Point Pain Score. Record if subject directed to come in for clinician evaluation. Record post-stent evaluation and photograph, if possible. Record Clinician Usability Survey forstent removal. If possible, subject will complete post-stent removal USSQ survey (attach to CFR) and 10-Point Pain Score.] Afterseveral cases of the Relief Stent, an optional supplemental questionnaire may be completed by the provider regarding the use of the research device.

Study Timeline

Assessment	Screening and Stent Placement (Day 0)	Post-Stent Placement (24-48 hrs)	Day of Stent Removal (Stent in situ, Day 7-30)	Post-Stent Removal
Informed Consent Form	X			
General Physical Examination	х	X [In-office or remote evaluation]	X [In-office]	
Current Medications	х	X [In-office or remote evaluation]	X [In-office]	
Vital Signs	х	X [In-office or remote evaluation]	X [In-office]	
Indicated for Ureteral Stenting	X			
Inclusion/Exclusion Criteria	Х			
Enrollment	X			
Ureteral Stent Symptoms Questionnaire	х	х	X [Before removal]	X [In-person or remote evaluation
RELIEF® Ureteral Stent	X [Placement]		X [Removal]	
Additional Therapies, if needed	×	x	x	ľ
Adverse Events	X	х	X	
Clinician Usability Survey	X [Placement]		X [Removal]	

Data to be Collected

- Patient demographics (Age, Sex, Race, BMI)
- Present and past history.
- Prior surgical procedures.
- Laboratory tests results,
- Any imaging results on the abdomen and pelvis.
- USSQ survey.

B. Intra-operative

- Total operative time
- Total fluoroscopy time
- Case Report forms as described before.

C. Post-operative

- USSQ survey.
- Case Report forms.
- Any complications/ adverse events.

[figure not shown]
Data Analysis Plan

Current enrollment number is designed to collect sufficient patient data to power a future, statisticallypowered clinical study to obtain an expanded FDA intended use claim for reduction in reflux and minimizes the potential for coil positioning on the trigone.

Study Endpoints:

1- Primary effectiveness endpoint:

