- Study success defined as adequate short term drainage defined as the presence of the stent in the ureter and the lack of surgical or other intervention to treat symptoms associated with the stent itself or failure of the stent on the stented side during the first 48 hours [Day 0-2] following placement. [Note: In some cases, the ureteral stent may not be sufficient to relieve pain (not associated with stent specifically) and alternative surgical treatment may be warranted. In these cases, patient data will be captured but non-device related cause captured as reason for subject stenting termination.]
- Assessment of retrograde urine reflux after placement of the RELIEF® Ureteral Stent, as determined by the visualization of urine in the distal ureter to the kidney using cystography after contrast gravity-filling of the bladder and assigning a urinary reflux grade based on:
 - Grade I: urine refluxes into the ureter only.
 - Grade II: urine refluxes into the ureter and up to the kidney without dilation.
 - Grade III: urine refluxes into the ureter and kidney and causes mild dilation.
 - Grade IV: urine refluxes into ureter and kidney and causes dilation without twisting of the ureter.
 - Grade V: urine refluxes into ureter and kidney and causes significant dilation with twisting of the ureter.

• Visualization of distal coil in bladder, after RELIEF Stent placement. Document placement using a cystoscope.

2- Primary safety endpoint:

• Assessment of adverse events (incidence, relationship to device, severity) attributed to the Ureteral Stent, compared to established adverse event rates from published clinical studies and FDA reportable event occurrences, compared to number of US annual ureteral stent placements. (No anticipated adverse events from Stent design; known complications from stenting may be observed.)

3- Secondary endpoint:

• USSQ Scale (Ureteral Stent Symptoms Questionnaire) [Time Frame: Day 0 (pre-stenting), 24-48 hours post-stent placement, and Day 7-30 prior to stent removal].

Stopping Rules: In the occurrence of any unexpected adverse events to the participants, the study team will hold study recruitment until the investigation is completed. Patients who experience unanticipated adverse events will have the RELIEF stent promptly removed.

Expected Adverse Events include:

- Flank pain/loin discomfort
- Flank pain when voiding
- Suprapubic pain/lower abdominal pain
- Trigonal irritation
- Urinary frequency
- Nocturia
- Urinary urgency

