The study will pay for all procedures/devices that are directly associated with this research study. This includes the RELIEF stent, and the extra x-rays. Procedures or drugs that are considered standard of care will be the responsibility of the patient or his/her insurance company

Research Participant Compensation

No compensation will be provided to study participants.

[figure not shown]
Provisions to Monitor the Data to Ensure the Safety of Research Participants

The group of investigators, including the principal investigator, and the research support staff (nurses, CMA's, data managers, and regulatory) will carry out the Data and Safety Monitoring Plan. Data will be reviewed quarterly to ensure that it is accurate, complete, and that its collection is in compliance with the protocol. There will also be a continual assessment of the risks and benefits.

Furthermore, Case report forms will be generated for each subject and completed by the investigator or study coordinator. The investigator or study coordinator will countersign each form. After the case report forms for a visit are completed, the research coordinator will enter a limited set of data into a data management system. Original case report forms will be securely maintained at the clinical sites. Completed copies of the case report forms will be sent to the research coordinator where they will be stored on the Shared "S" Drive. Subjects will be asked to report any adverse events to the study coordinator or physician. All adverse events will be reported on a standardized form that will elicit the number and specify the type of tests used, therapy (or therapies) used, and clinical visits (office, ER and hospitalization) required until the event is resolved.

[figure not shown]
DEVICE DESCRIPTION:

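### The primary safety comparison sets openly reported symptom events against published rates that need not have been collected the same way, and leaves the USSQ out

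*Protocol*

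**What the plan says.** **Endpoint and comparator.** In Study Endpoints, the primary safety endpoint is the incidence, device relationship and severity of adverse events put down to the stent. The yardstick is external; these events are to be "compared to established adverse event rates from published clinical studies and FDA reportable event occurrences". No reference rate, margin or test is named. The design is one open-label group (Study Design), with 20 to 30 patients (Number of Research Participants).

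**Which events.** The list of expected adverse events has 17 entries. Ten are symptoms: two kinds of flank pain, suprapubic pain, frequency, nocturia, urgency, dysuria, urethral discomfort, incontinence and hematuria. The only published symptom rate in the protocol is in Background, where stent symptoms are described so: "they can occur in up to 80% of stented patients".

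**How events are found.** The data-monitoring section says: "Subjects will be asked to report any adverse events to the study coordinator or physician". On recording it says: "All adverse events will be reported on a standardized form that will elicit the number and specify the type of tests used". The form also covers therapies and clinical visits. The Study Timeline row "Adverse Events" is marked at Day 0, at 24-48 hours and on the day of removal.

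**What else is measured.** Study Procedures has every patient complete the USSQ and a 10-point pain score before stenting, at 24-48 hours and before removal on day 7-30. The USSQ is a separate secondary endpoint. No text says when a USSQ answer becomes an adverse event, or how a symptom already present on Day 0 is counted.

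**The concern.** With no concurrent control, the published rates are the only benchmark for symptom events. The comparison is informative only if both sides count symptoms in a similar way. The protocol fixes one side as a general request to report, recorded on a form whose named content is tests, therapies and visits. It asks nothing of the other side.

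Two features unrelated to the stent can then move the result:

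- **Capture.** If a general request picks up fewer symptoms than the method behind the published rate, the trial's incidence falls below that rate with no true difference. If it picks up more, the reverse happens.
- **Day 0 status.** Patients enter with a stone or stricture and may already have these symptoms. Leaving such symptoms out lowers the incidence, and counting them raises it.

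The protocol hypothesises fewer irritative bladder symptoms with this stent and the study is open label. A low symptom count would readily be read as support for the device.

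**Working it through.** The protocol gives no figure for this comparison, so there is nothing to reproduce. The following shows only how far incomplete capture could carry the result.

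**Inputs from the protocol:** n = 20 and n = 30; reference rate 0.80, the Background figure, which is an upper value for any symptom.

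**Assumptions:** the true rate equals the reference; a share c of patients with symptoms is recorded as having an event (c from 1.0 down to 0.5); the result counts as favouring the stent if the upper limit of the exact two-sided 95% Clopper-Pearson interval is below the reference.

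**Step 1, cut-off.** The upper limit for x events in n patients is the 97.5% quantile of Beta(x+1, n−x). It is below 0.80 for x ≤ 11 of 20 (limit 0.769 at x = 11) and for x ≤ 18 of 30 (limit 0.773 at x = 18).

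**Step 2, probability.** The recorded rate is p = 0.80 × c. The probability is P(X ≤ 11) with X ~ Bin(20, p), or P(X ≤ 18) with X ~ Bin(30, p).

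| Capture c | p | n = 20 | n = 30 |
|---|---|---|---|
| 1.0 | 0.80 | 0.010 | 0.010 |
| 0.9 | 0.72 | 0.078 | 0.106 |
| 0.8 | 0.64 | 0.268 | 0.389 |
| 0.7 | 0.56 | 0.550 | 0.732 |
| 0.6 | 0.48 | 0.802 | 0.933 |
| 0.5 | 0.40 | 0.944 | 0.992 |

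**Step 3, other reference rates.** With c = 0.7 and the true rate again equal to the reference, the cut-off is recalculated for each rate.

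| Reference (assumed) | n = 20 | n = 30 |
|---|---|---|
| 0.60 | 0.346 | 0.489 |
| 0.40 | 0.147 | 0.224 |
| 0.20 | 0.049 | 0.064 |

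**Step 4, Day 0 symptoms.** Assume 20% of patients have the symptom on Day 0.

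- If these patients are not counted while the published 0.80 counts everyone with the symptom, the recorded rate is 0.80 − 0.20 = 0.60. The interval lies wholly below 0.80 with probability 0.404 (n = 20) or 0.569 (n = 30).
- If they are counted while the published rate is for new symptoms only (assumed 0.50), the recorded rate is 0.50 + 0.20 = 0.70. The interval lies wholly above 0.50 with probability 0.416 or 0.589.

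So the Day 0 question can push the result either way.

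**The case against.** Several stronger readings are tempting, and the protocol does not support them.

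- **That events are merely volunteered.** Patients are asked, adverse events are scheduled at three contacts, and a clinician evaluates the patient at 24-48 hours and at removal. What is missing is narrower: a symptom-by-symptom prompt, or a rule linking USSQ answers to events.
- **That the bias must favour the stent.** No text shows that a general request captures less than the published studies did; that is an assumption. Day 0 symptoms can act in either direction.
- **That 80% is the planned comparator and was obtained by questionnaire.** The endpoint names no rate. The cited source with the USSQ in its title supports the statement on distal coils crossing the midline, not the 80%. How any comparator rate was collected is not stated.
- **That pre-existing symptoms go unfiltered.** The endpoint is restricted to events attributed to the stent, and Day 0 status is available to inform that judgement. The detailed rule could be set in an analysis plan that is not shown.

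It is also fair to say that the calculation uses a decision rule the protocol does not contain, in a study meant to inform a later powered trial. Replacing event reports by the USSQ would bring its own faults: two time points with the stent in place can miss transient symptoms, device relationship would be lost, and the USSQ items are not shown.

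These objections limit the claim. They do not remove it: the protocol fixes both the collection method and the external comparison, and asks for no match between them. An analysis plan could not recover unrecorded symptoms without turning to the USSQ.

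**Conclusion.** The point holds in limited form. As written, a difference between this trial's symptom events and published symptom rates, whether lower or higher, cannot be assigned to the stent, because it may come from the method of collection or from symptoms present on Day 0.

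The size is unknown and depends on assumed capture. It is negligible at full capture, modest at 90% and large at 70% if the reference is near 80%; it shrinks markedly for symptoms with low reference rates. The protocol does not establish that the comparison will favour the device. The weakness concerns symptom terms; migration, encrustation, infection and additional procedures are outside it. It merits a change because the data for a better comparison are already being collected.

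**What to change.** 1. Keep attributed adverse event reporting for all events, symptoms included, with relationship and severity.
2. For each symptom term that the USSQ covers, add incidence from the USSQ at 24-48 hours and before removal. Show it twice: symptom present, and symptom new or worse than that patient's Day 0 answer. Check term by term which of the listed symptoms the questionnaire covers.
3. Restrict the external symptom comparison to published rates obtained by questionnaire at a similar time with the stent in place, matching the published definition (present, or new). Where no such rate exists, report symptom adverse events descriptively and make no comparison.

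**Cost:** revised endpoint wording and some extra analysis. No added visits or patients are needed, because the USSQ is already scheduled. Fewer published studies will qualify as comparators, and the symptom rates may look less favourable than those from open reporting.
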